## APPENDIX 3: CONTRACEPTION

### Male Participant Reproductive Inclusion Criteria

Male participants are eligible to participate if they agree to the following requirements during the intervention period and for at least 90 days after the last dose of study drug, which corresponds to the time needed to eliminate reproductive safety risk of the study intervention(s):

- Refrain from donating sperm.

PLUS either:

- Be abstinent from heterosexual intercourse with a woman of childbearing potential as their preferred and usual lifestyle (abstinent on a long-term and persistent basis) and agree to remain abstinent.

OR

- Must agree to use a male condom when engaging in any activity that allows for passage of ejaculate to another person.
- In addition to male condom use, a highly effective method of contraception may be considered in WOCBP partners of male participants (refer to the list of highly effective methods below).

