## 5 STUDY POPULATION

### 5.1 INCLUSION CRITERIA

Participants must meet all of the following criteria to be eligible for participation in this study:

1. In the opinion of the Investigator, the participant is capable of understanding and complying with protocol requirements.
2. The participant is willing to sign and date a written, informed consent form and any required privacy authorization prior to the initiation of any study procedures, including requesting that a participant fast for any laboratory evaluations.
3. The participant is a healthy adult male or female aged 18 to 45 years, inclusive, at the time of informed consent.
4. The participant weighs between 45 kg (99 lbs) and 100 kg (220 lbs) and has a body mass index (BMI) between 18.0 and 30.0 kg/m^2, inclusive, at the time of informed consent.
5. The participant has physical examination, clinical laboratory values, and ECG results that are clinically acceptable. Laboratory results outside of the reference range must be documented as acceptable by the Investigator and Sponsor.
6. A male participant who is nonsterilized and sexually active with a female partner of childbearing potential must agree to use highly effective contraception from the time of signing the informed consent throughout the duration of the study, and for 90 days after the last dose of study drug. See [Appendix 3](#) for details on contraception requirements during the study.
7. A female participant of childbearing potential who is sexually active with a nonsterilized male partner agrees to routinely use highly effective contraception from the time of signing the informed consent, throughout the duration of the study, and for 90 days after the last dose of study drug. See [Appendix 3](#) for details on contraception requirements during the study.

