### 5.2 EXCLUSION CRITERIA

Participants who meet any of the following exclusion criteria will not be eligible for participation in this study:

1. The participant has received any investigational compound within 90 days before dosing.
2. The participant is an immediate family member, CRU employee, or is in a dependent relationship with a CRU employee who is involved in the conduct of this study (eg, spouse, parent, child, sibling) or may consent under duress.

3. The participant has any clinically significant illness, such as cardiovascular, neurologic, pulmonary, hepatic, renal, metabolic, gastrointestinal, urologic, immunologic, endocrine, or psychiatric disease or disorder, or other abnormality, which may affect the participant's safety, increase risk of seizure or lower the seizure threshold, or potentially confound the study results. It is the responsibility of the Investigator to assess the clinical significance of any conditions the participant may have; however, consultation with the Xentria Medical Monitor may be warranted.
4. The participant has a known hypersensitivity to any component of the formulation of XTMAB-16.
5. The participant has a positive result for drugs of abuse (defined as any illicit drug use) or alcohol at Screening or Baseline (Day -2).
6. The participant has a history of drug abuse (defined as any illicit drug use) or a history of alcohol abuse within 1 year prior to Screening or is unwilling to agree to abstain from alcohol and drugs throughout the study.
7. The participant has taken any excluded medication, supplements, or food products during the time periods listed in [Table 4](#).
8. If female, the participant is pregnant or lactating or intends to become pregnant before, during, or within 90 days after the last dose of study drug or intending to donate ova during such time period.
9. If male, the participant intends to donate sperm during the study or within 90 days after the last dose of study drug.
10. The participant has a history of autoimmune disease or respiratory disorders.
11. The participant or any immediate family member has a history of cancer, except basal cell carcinoma, that has not been in remission for at least 5 years prior to Baseline (Day -2).
12. The participant has a condition that can potentially reduce drug clearance (eg, renal or hepatic insufficiency).
  - a. Glomerular filtration rate <60
  - b. ALT >41 U/L
  - c. AST > 34 U/L
  - d. Alkaline phosphatase >117 U/L
  - e. Total protein >8.2 g/dL

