#### 5.5 REPLACEMENT OF PARTICIPANTS

- Participants who sign the informed consent form and are randomized but do not receive the study intervention may be replaced.

- Participants who sign the informed consent form, are randomly assigned to treatment, receive the study intervention, and subsequently withdraw or are withdrawn or discontinued from the study before Week 2, will be replaced.
- Participants who are lost-to-follow-up will be replaced.

Replacement participants will be assigned to the same treatment assignment as the participant who discontinued.

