### **Contraception Methods**

Contraceptive use by men or women should be consistent with local availability/regulations regarding the use of contraceptive methods for those participating in clinical trials.

Highly effective methods (according to Therapeutics Research Program Guidance for the Development of Protocol Procedures to Address Reproductive Risk, 21 Dec 2017):

- Bilateral tubal ligation or tubal occlusion
- An approved hormonal contraceptive such as oral contraceptives, patches, implants, injections, rings, or hormonally-impregnated intrauterine device (IUD)
- IUD
- Vasectomized partner
  - Vasectomized partner is a highly effective contraceptive method provided that the partner is the sole sexual partner of the WOCBP and the absence of sperm

has been confirmed. If not, an additional highly effective method of contraception should be used. The spermatogenesis cycle is approximately 90 days.

- Sexual abstinence
  - Sexual abstinence is considered a highly effective method only if defined as refraining from heterosexual intercourse during the entire period of risk associated with the study intervention. The reliability of sexual abstinence needs to be evaluated in relation to the duration of the study and the preferred and usual lifestyle of the participant.

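### Appendix 3 makes a highly effective contraceptive method optional for sexually active, nonsterilized men, while inclusion criterion 6 makes it mandatory

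*Protocol*

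**What the plan says.** Section 5.1 of the Protocol opens with "Participants must meet all of the following criteria to be eligible for participation in this study". Under criterion 6, a nonsterilized man whose sexual partner is a WOCBP "must agree to use highly effective contraception from the time of signing the informed consent throughout the duration of the study", and then for 90 days after the last dose. The criterion refers to Appendix 3 for the details.

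The male part of Appendix 3 is worded as an eligibility rule of its own: "Male participants are eligible to participate if they agree to the following requirements during the intervention period". The same sentence extends the duty to a minimum of 90 days beyond dosing. The requirements are no sperm donation, plus one of two routes. The first is abstinence as the man's usual way of life. The second is the condom route: "Must agree to use a male condom when engaging in any activity that allows for passage of ejaculate to another person". The last bullet on that route adds that, beyond the condom, "a highly effective method of contraception may be considered in WOCBP partners of male participants".

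The list of highly effective methods at the end of Appendix 3 has five entries: tubal ligation or occlusion, approved hormonal contraceptives, an IUD, a vasectomized partner, and sexual abstinence. The male condom is not among them.

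**The concern.** The criterion imposes a duty and the appendix turns the same duty into a suggestion. Because criterion 6 points to the appendix for its content, a site checking a man's eligibility may well work from the appendix. It could then enrol someone who uses condoms only and so fails criterion 6. That would be an inclusion deviation on a rule meant to protect a partner and a possible pregnancy, in the first study of this antibody in humans. The appendix itself ties the 90 days to clearing reproductive risk, and Section 8.6.7 has pregnancies in partners of male participants reported within 24 hours of the investigator learning of them.

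**Working it through.** The plan states no figure on this point, so the check is mainly a comparison of texts.

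**1. One man, two answers.** Take a nonsterilized man, sexually active with a WOCBP partner, who uses condoms, does not donate sperm, and whose partner uses no listed method.

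| Question | Section 5.1, criterion 6 | Appendix 3, male section |
|---|---|---|
| Highly effective method | Required | Optional |
| Condom | Not mentioned | Required, any partner |
| Condom counts as highly effective? | Defers to Appendix 3 | Not on the list |
| Start of the duty | Signing of consent | Intervention period (not defined) |
| End of the duty | 90 days after last dose | At least 90 days after last dose |
| Is this man eligible? | No | Yes |

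**2. Where the conflict stops.** A man who abstains can satisfy both texts, since "Sexual abstinence is considered a highly effective method only if defined as refraining from heterosexual intercourse during the entire period of risk", and he can commit to that for the whole period. Appendix 3 is stricter than criterion 6 in two respects: its condom rule covers any partner, and it bars sperm donation. The second agrees with exclusion criterion 9 ("If male, the participant intends to donate sperm during the study or within 90 days after the last dose of study drug"). Neither is in dispute.

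**3. What was probably intended.** The female section of Appendix 3 makes a highly effective method mandatory and agrees with criterion 7. Only the male section departs from its criterion.

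**4. Exposure and duration, for context.**

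- Planned active: 9 × 2 = 18. Planned placebo: 3 × 2 = 6. Active share: 18/24 = 75% (Protocol Section 4.1, Table 2).
- Criterion 6 window: up to 28 days from consent to the single dose, plus 90 days after it, is 28 + 90 = up to 118 days.
- The window ends on Day 1 + 90 = Day 91, which is 91 − 71 = 20 days after the last scheduled visit.

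The end date is common to both texts. Any difference in start date depends on how the intervention period is read, and would fall before dosing.

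**5. Effect on the analysis sets.** None of the definitions in SAP Section 4.5 mentions contraception. The PK per-protocol set drops participants only for important deviations in drug administration that would affect concentration. The Biomarker Set drops them only for major deviations in drug administration. The other sets have no deviation exclusion. SAP Section 4.4.2 does list eligibility deviations and leaves exclusions to the data review meeting, so an effect is not formally closed off, but none is expected.

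**The case against.** The best defence is that the two texts can be obeyed together. Section 5.1 requires every criterion to be met, criterion 6 is explicit, and the appendix does not forbid a highly effective method. A site that applies the stricter text enrols nobody wrongly, and eligibility is checked at both Screening and Baseline. Mandatory condoms and the bar on sperm donation also cover part of the risk. This is why the point is minor. It does not remove the conflict: neither text says that the stricter one prevails, and the appendix states an eligibility rule that gives the wrong answer.

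A second objection is that the day counts and the 75% do not measure the defect. That is fair. They describe whom the rule protects and for how long, not the size of the discrepancy.

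A third is that a new bullet starting at consent would sit under a lead-in that starts at the intervention period. The bullet suggested below states its own start and end, so it works under the present lead-in. Aligning the lead-in as well would be tidier but is not needed. Abstinence also appears on the list the bullet points to. A man covered by the bullet cannot rely on it while sexually active, so its presence does no harm.

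**Conclusion.** The concern holds. For nonsterilized men who stay sexually active with a WOCBP partner and rely on condoms without a listed method, criterion 6 and Appendix 3 give opposite eligibility answers. Since all Section 5.1 criteria must be met, the appendix is wrong as written.

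The number of men affected is unknown: the documents give no sex quota and no data on contraceptive use. About three quarters of any such men would be expected to receive XTMAB-16 under the planned allocation. Neither 24 participants nor 18 on active drug is a firm ceiling, because under Section 5.5 randomized participants who "receive the study intervention, and subsequently withdraw or are withdrawn or discontinued from the study before Week 2, will be replaced". The 118-day figure assumes a single screening period of at most 28 days; Section 5.4 allows one rescreen and does not say whether consent is renewed. No statistical result is expected to change.

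**What to change.** Replace only the last male bullet in Appendix 3 with a mandatory one. Suggested content: *On top of the condom, any nonsterilized man who is sexually active with a WOCBP partner must agree that one of the highly effective methods listed below will be in use from the day he signs consent, for the whole study, and until at least 90 days after his last dose.*

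Criterion 6 and the lead-in, sperm-donation, abstinence and condom text in Appendix 3 can stay as they are. The new bullet carries criterion 6's requirement and period, and adds no duty for sterilized men or for men without a WOCBP partner.

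The cost is one sentence in a protocol amendment, with no change to design, sample size or analysis. The consent form should be checked for the same wording; it was not available for this review.

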### Female Participant Reproductive Inclusion Criteria

A female participant is eligible to participate whether she is of childbearing potential or is postmenopausal (see definitions below). A female participant of childbearing potential who is sexually active with a nonsterilized male partner **must** agree to use highly effective contraception from the time of signing the informed consent, throughout the duration of the study, and for 90 days after the last dose of study drug.

The Investigator is responsible for review of medical history, menstrual history, and recent sexual activity to decrease the risk for inclusion of a woman with an early undetected pregnancy.

### Woman of Childbearing Potential

A woman is considered fertile following menarche and until becoming postmenopausal unless permanently sterile (see below).

If fertility is unclear (eg, amenorrhea in adolescents or athletes) and a menstrual cycle cannot be confirmed before the first dose of study intervention, additional evaluation should be considered.

Women in the following categories are not considered WOCBP:

1. Premenopausal female with 1 of the following:

- a. Documented hysterectomy
- b. Documented bilateral salpingectomy
- c. Documented bilateral oophorectomy

For individuals with permanent infertility due to an alternate medical cause other than the above, (eg, Müllerian agenesis, androgen insensitivity), Investigator discretion should be applied to determining study entry.

Note: Documentation for any of the above categories can come from the CRU personnel's review of the participant's medical records, medical examination, or medical history interview. The method of documentation should be recorded in the participant's medical record for the study.

2. Postmenopausal female.

- a. A postmenopausal state is defined as no menses for 12 months without an alternative medical cause. In addition:
  - i. A high follicle stimulating hormone (FSH) level in the postmenopausal range must be used to confirm a postmenopausal state in women under 60 years old and not using hormonal contraception or hormone replacement therapy (HRT).
  - ii. Woman on HRT and whose menopausal status is in doubt will be required to use one of the nonestrogen hormonal highly effective contraception methods if they wish to continue their HRT during the study. Otherwise, they must discontinue HRT to allow confirmation of postmenopausal status before study enrollment.

### **Contraception Methods**

Contraceptive use by men or women should be consistent with local availability/regulations regarding the use of contraceptive methods for those participating in clinical trials.

Highly effective methods (according to Therapeutics Research Program Guidance for the Development of Protocol Procedures to Address Reproductive Risk, 21 Dec 2017):

- Bilateral tubal ligation or tubal occlusion
- An approved hormonal contraceptive such as oral contraceptives, patches, implants, injections, rings, or hormonally-impregnated intrauterine device (IUD)
- IUD
- Vasectomized partner
  - Vasectomized partner is a highly effective contraceptive method provided that the partner is the sole sexual partner of the WOCBP and the absence of sperm

has been confirmed. If not, an additional highly effective method of contraception should be used. The spermatogenesis cycle is approximately 90 days.

- Sexual abstinence
  - Sexual abstinence is considered a highly effective method only if defined as refraining from heterosexual intercourse during the entire period of risk associated with the study intervention. The reliability of sexual abstinence needs to be evaluated in relation to the duration of the study and the preferred and usual lifestyle of the participant.

**APPENDIX 4: TOXICITY GRADING FOR INJECTION SITE REACTIONS, VITAL SIGNS, AND LABORATORY PARAMETERS**

**Table 9      Grading for Injection Site Reactions**

Local Reaction to Injectable Product	Mild (Grade 1)	Moderate(Grade 2)	Severe (Grade 3)	Potentially Life Threatening (Grade 4)
Pain	Does not interfere with activity	Repeated use of non-narcotic pain reliever > 24 hours or interferes with activity	Any use of narcotic pain reliever or prevents daily activity	Emergency room (ER) visit or hospitalization
Tenderness	Mild discomfort to touch	Discomfort with movement	Significant discomfort at rest	ER visit or hospitalization
Erythema/Redness *	2.5 – 5 cm	5.1 – 10 cm	> 10 cm	Necrosis or exfoliative dermatitis
Induration/Swelling **	2.5 – 5 cm and does not interfere with activity	5.1 – 10 cm or interferes with activity	> 10 cm or prevents daily activity	Necrosis

\* In addition to grading the measured local reaction at the greatest single diameter, the measurement should be recorded as a continuous variable.

\*\* Induration/Swelling should be evaluated and graded using the functional scale as well as the actual measurement.

**Table 10      Grading for Vital Signs**

Vital Signs *	Mild (Grade 1)	Moderate(Grade 2)	Severe (Grade 3)	Potentially Life Threatening (Grade 4)
Fever (°C) ** (°F) **	38.0 – 38.4 100.4 – 101.1	38.5 – 38.9 101.2 – 102.0	39.0 – 40 102.1 – 104	> 40 > 104
Tachycardia - beats per minute	101 – 115	116 – 130	> 130	ER visit or hospitalization for arrhythmia
Bradycardia - beats per minute***	50 – 54	45 – 49	< 45	ER visit or hospitalization for arrhythmia
Hypertension (systolic) - mm Hg	141 – 150	151 – 155	> 155	ER visit or hospitalization for malignant hypertension
Hypertension (diastolic) - mm Hg	91 – 95	96 – 100	> 100	ER visit or hospitalization for malignant hypertension
Hypotension (systolic) – mm Hg	85 – 89	80 – 84	< 80	ER visit or hospitalization for hypotensive shock
Respiratory Rate – breaths per minute	17 – 20	21 – 25	> 25	Intubation

\* Subject should be at rest for all vital sign measurements.

\*\* Oral temperature; no recent hot or cold beverages or smoking.

\*\*\* When resting heart rate is between 60 – 100 beats per minute. Use clinical judgement when characterizing bradycardia among some healthy subject populations, for example, conditioned athletes.

**Table 11      Grading for Clinical Abnormalities**

Serum *	Mild (Grade 1)	Moderate (Grade 2)	Severe (Grade 3)	Potentially Life Threatening (Grade 4) **
Sodium – Hyponatremia mEq/L	132 – 134	130 – 131	125 – 129	< 125
Sodium – Hypernatremia mEq/L	144 – 145	146 – 147	148 – 150	> 150
Potassium – Hyperkalemia mEq/L	5.1 – 5.2	5.3 – 5.4	5.5 – 5.6	> 5.6
Potassium – Hypokalemia mEq/L	3.5 – 3.6	3.3 – 3.4	3.1 – 3.2	< 3.1
Glucose – Hypoglycemia mg/dL	65 – 69	55 – 64	45 – 54	< 45
Glucose – Hyperglycemia				Insulin requirements or hyperosmolar coma
Fasting – mg/dL	100 – 110	111 – 125	>125	
Random – mg/dL	110 – 125	126 – 200	>200	
Blood Urea Nitrogen BUN mg/dL	23 – 26	27 – 31	> 31	Requires dialysis
Creatinine – mg/dL	1.5 – 1.7	1.8 – 2.0	2.1 – 2.5	> 2.5 or requires dialysis
Calcium – hypocalcemia mg/dL	8.0 – 8.4	7.5 – 7.9	7.0 – 7.4	< 7.0
Calcium – hypercalcemia mg/dL	10.5 – 11.0	11.1 – 11.5	11.6 – 12.0	> 12.0
Magnesium – hypomagnesemia mg/dL	1.3 – 1.5	1.1 – 1.2	0.9 – 1.0	< 0.9
Phosphorous – hypophosphatemia mg/dL	2.3 – 2.5	2.0 – 2.2	1.6 – 1.9	< 1.6
CPK – mg/dL	1.25 – 1.5 x ULN***	1.6 – 3.0 x ULN	3.1 – 10 x ULN	> 10 x ULN
Albumin – Hypoalbuminemia g/dL	2.8 – 3.1	2.5 – 2.7	< 2.5	--
Total Protein – Hypoproteinemia g/dL	5.5 – 6.0	5.0 – 5.4	< 5.0	--
Alkaline phosphate – increase by factor	1.1 – 2.0 x ULN	2.1 – 3.0 x ULN	3.1 – 10 x ULN	> 10 x ULN
Liver Function Tests –ALT, AST increase by factor	1.1 – 2.5 x ULN	2.6 – 5.0 x ULN	5.1 – 10 x ULN	> 10 x ULN
Bilirubin – when accompanied by any increase in Liver Function Test increase by factor	1.1 – 1.25 x ULN	1.26 – 1.5 x ULN	1.51 – 1.75 x ULN	> 1.75 x ULN
Bilirubin – when Liver Function Test is normal; increase by factor	1.1 – 1.5 x ULN	1.6 – 2.0 x ULN	2.0 – 3.0 x ULN	> 3.0 x ULN
Cholesterol	201 – 210	211 – 225	> 226	---
Pancreatic enzymes – amylase, lipase	1.1 – 1.5 x ULN	1.6 – 2.0 x ULN	2.1 – 5.0 x ULN	> 5.0 x ULN

\* The laboratory values provided in the tables serve as guidelines and are dependent upon institutional normal parameters. Institutional normal reference ranges should be provided to demonstrate that they are appropriate.

\*\* The clinical signs or symptoms associated with laboratory abnormalities might result in characterization of the laboratory abnormalities as Potentially Life Threatening (Grade 4). For example, a low sodium value that falls within a grade 3 parameter (125-129 mEq/L) should be recorded as a grade 4 hyponatremia event if the subject had a new seizure associated with the low sodium value.

\*\*\*ULN" is the upper limit of the normal range.

Source: FDA Guidance for Industry: Toxicity Grading Scale for Healthy Adult and Adolescent Volunteers enrolled in Preventive Vaccine Clinical Trials. September 2007.

## APPENDIX 5: CRITERIA FOR DIAGNOSING AND RECOMMENDED TREATMENT FOR ANAPHYLAXIS

**Table 12 Clinical Criteria for Diagnosing Anaphylaxis**

**Anaphylaxis is highly likely when any one of the following 3 criteria are fulfilled:**

[figure not shown]
1. Acute onset of an illness (minutes to several hours) with involvement of the skin, mucosal tissue, or both (eg, generalized hives, pruritus or flushing, swollen lips-tongue-uvula)  
*AND AT LEAST ONE OF THE FOLLOWING*
  - a. Respiratory compromise (eg, dyspnea, wheeze-bronchospasm, stridor, reduced PEF, hypoxemia)
  - b. Reduced BP or associated symptoms of end-organ dysfunction (eg, hypotonia [collapse], syncope, incontinence)
2. Two or more of the following that occur rapidly after exposure to a *likely allergen for that patient* (minutes to several hours):
  - a. Involvement of the skin-mucosal tissue (eg, generalized hives, itch-flush, swollen lips-tongue-uvula)
  - b. Respiratory compromise (eg, dyspnea, wheeze-bronchospasm, stridor, reduced PEF, hypoxemia)
  - c. Reduced BP or associated symptoms (eg, hypotonia [collapse], syncope, incontinence)
  - d. Persistent gastrointestinal symptoms (eg, crampy abdominal pain, vomiting)
3. Reduced BP after exposure to *known allergen for that patient* (minutes to several hours):
  - a. Infants and children: low systolic BP (age specific) or greater than 30% decrease in systolic BP\*
  - b. Adults: systolic BP of less than 90 mm Hg or greater than 30% decrease from that person's baseline

*PEF*, Peak expiratory flow; *BP*, blood pressure.

\*Low systolic blood pressure for children is defined as less than 70 mm Hg from 1 month to 1 year, less than  $(70 \text{ mm Hg} + [2 \times \text{age}])$  from 1 to 10 years, and less than 90 mm Hg from 11 to 17 years.

Source: Sampson HA, Muñoz-Furlong A, Campbell RL, et al. Second symposium on the definition and management of anaphylaxis: Summary report – Second National Institute of Allergy and Infectious Disease/Food Allergy and Anaphylaxis Network symposium. *Am Acad Allergy, Asthma, Immunol.* 2006.

**Figure 2** Algorithm for the Treatment of Acute Anaphylaxis

Abbreviations: ACLS = advanced cardiac life support; CPR = cardiopulmonary resuscitation; ICU = intensive care unit.

Source: Lieberman P, Kemp SF, Oppenheimer J, et al. The diagnosis and management of anaphylaxis: An updated practice parameter. *Am Acad Allergy, Asthma, Immunol*. 2005.
